IRB Minimal Risk Protocol Template

Note: If this study establishes a human specimen repository (biobank) for research purposes, do not use this template. Use the Mayo Clinic Human Specimen Repository Protocol Template found on the IRB home page under Forms and Procedures at http://intranet.mayo.edu/charlie/irb/

First-time Use: Use this template to describe your study for a new IRB submission.

- 1. Complete the questions that apply to your study.
- 2. Save an electronic copy of this protocol for future revisions.
- 3. When completing your IRBe application, you will be asked to upload this document to the protocol section.

Modification: To modify this document after your study has been approved:

- 1. Open your study in IRBe. Click on the study 'Documents' tab and select the most recent version of the protocol. Save it to your files.
- 2. Open the saved document and activate "Track Changes".
- 3. Revise the protocol template to reflect the modification points, save the template to your files
- 4. Create an IRBe Modification for the study and upload the revised protocol template.

General Study Information

Principal Investigator: [name]

Study Title: A Randomized-Controlled trial comparing long-acting and short-acting local anesthetics at the time of penile prosthesis placement.

Protocol version number and date: Version 2; July 21, 2021

Research Question and Aims

Hypothesis:

Local anesthesia with liposomal bupivacaine administered at the time of penile prosthesis placement will reduce postoperative opioid use and decrease post-operative pain when compared with administration of ropivacaine.

Aims, purpose, or objectives:

This study aims to determine if using liposomal bupivacaine, when compared with ropivacaine, for postoperative pain control in patients undergoing surgical placement of a 3-piece inflatable penile prosthesis is associated with less overall opioid use and lower postoperative pain scores during the early postoperative period. Variables to be analyzed will include pre- and postoperative pain and anxiety scores, in-hospital (if-applicable) and home opioid use postoperatively, and adverse intraoperative, perioperative, and postoperative events.

Background (Include relevant experience, gaps in current knowledge, preliminary data, etc.):

The United States is in the midst of an opioid epidemic, with prescription-related drug deaths at an all time high over the last decade. Surgeons are responsible for a significant proportion of opioid prescribing for postoperative pain control, and it is estimated that 2-6% of patients who receive opioids postoperatively may go on to develop persistent use or dependence.[1,2] To this end, urology has been at the forefront in attempts to develop extended recovery after surgery (ERAS) protocols to optimize pain control while minimizing the need for opioid medications.

Penile prosthesis placement is considered the gold standard for the management of men with medication-refractory erectile dysfunction (ED). It is associated with high levels of patient and partner satisfaction and restores the ability for a patient to engage in satisfactory sexual activity.[3] Multiple innovations in device technology and operative approach have minimized adverse events such as device infection and mechanical malfunction, making this a highly effective and reproducible treatment for men with severe ED.[4] The procedure itself can be associated with significant perioperative and postoperative pain due to the high density of pain receptors located within the penis, scrotum, and inguinal regions. Historically, many prosthetic surgeons have compensated for this by prescribing large quantities of opioids to be used for breakthrough pain. However, in the era of increasing awareness regarding the negative effects of opioid medications, there has been renewed interest in alternative pain control regimens. For example, Lucas et al found that postoperative pain scores and opioid use were significantly lower in patients who underwent penile prosthesis placement with a multi-modal pain regimen that included acetaminophen, meloxicam or celecoxib, and gabapentin and intraoperative dorsal and pudendal nerve blocks with lidocaine/bupivacaine.[5] This and another novel approaches are appealing, but clinical experience has revealed short-comings with pain control regimens based on short-acting local anesthetics such as lidocaine/bupivacaine, wherein the local effects may wane within several hours. Neuroleptics including gabapentin are also suboptimal due to untoward side-effects including sedation and even adverse anesthesia events such as prolonged sedation requiring a longer stay in the postoperative recovery unit. For these reasons, a longer-activing local anesthetic is particularly appealing from both safety and efficacy perspectives.

Liposomal bupivacaine (LB) is a long-acting local anesthetic that has been shown to promote local pain control in the postoperative period for up to 72 hours, as compared to traditional local anesthetic agents with half-lives ranging from 1-6 hours. The prolonged pain control duration is the result of suspending the bupivacaine within a lipid vessel that creates slow release of the medication within tissues over time. Within the realm of urology very few studies have assessed outcomes in patients who receive perioperative LB. A study by Cotta et al from 2016 retrospectively explored their experience with LB (n=13) compared with those receiving local bupivacaine (n=24) for anesthesia during penile prosthesis placement.[6] The authors found that patients receiving LB used significantly fewer opioids postoperatively. Two additional studies by Alom et al and [name] et al described LB for use with office-based surgical procedures involving the penis and scrotum, although outcomes related to pain control were not specifically evaluated.[7,8] Finally, a recent study by Taniguchi and Mulhall showed that LB did not adversely impact systemic hemodynamics when administered within the corpora cavernosa of patients at the time of penile prosthesis placement, supporting the safety of this medication in the perioperative setting.[9]

It has been our experience that LB optimizes pain control in the postoperative setting when administered at the time of penile prosthesis placement. This has become a routine part of clinical practice. However, LB results in added expense, and to date there has never been an adequately powered prospective study comparing outcomes between LB and other shorter-acting local anesthestics to determine if this added expense is justified. Therefore, we intend to assess perioperative and postoperative outcomes including safety and pain control in patients who receive local anesthesia with LB versus ropivacaine at the time of penile prosthesis placement.

References:

Study participants will be randomized to one of two study arms. Arm 1 will receive 40 mL of ropivicaine to be used for local anesthetic infiltration. Arm 2 will receive 40 mL of Liposomal bupivacaine (20 mL Exparel + 10 mL 0.25% bupivacaine) to be used for local anesthetic infiltration. The patient will be blinded to which study arm he is randomized to, but the surgeon will be aware (i.e. single blind). The specific agent (determined by study randomization) will be ordered by the performing surgeon through the "prep for case" inflatable penile prosthesis order set within EPIC. Two standardized order sets will be shared amongst the three performing surgeons and will also include standardized perioperative medication administration per a previously published enhanced recovery protocol (see reference #5 – Lucas et al).

Local anesthetic will be administered via a standard protocol at the time of penile prosthesis surgery. The block itself will include pudendal, scrotal, dorsal penile, and inguinal nerve blocks. The remainder of the penile prosthesis surgery will be per standard practice, with all surgeons currently utilizing a similar penoscrotal

approach. Of note, patients who currently receive intraoperative LB routinely wear a disposable bracelet with information for medical professionals regarding the recent receipt of this medication. This is worn for 72-96 hours postoperatively. For the study protocol, we will work with the perioperative nursing team to apply a similar bracelet describing the research study and acknowledging that each patient may have received LB versus ropivacaine during the surgery.

If the study coordinator is unable to meet with the patient to review consent, they will be a digital consent via email. The patient will be contacted by telephone and read a script about study participation. Patients will then have the ability to sign the consent form with their personal device. These digital consent forms will be stored in Ptrax.

If patients decide to consent digitally, they will be asked to complete the baseline requirements over the phone. These documents are the baseline anxiety inventory and the pain catastrophizing scale which will be recorded by the study coordinator.

Preoperative patient data including pertinent demographics as well as a baseline anxiety inventory and pain catastrophizing scale will be collected. They will also receive a medication log to track their narcotic intake until post-operative day 14. The patients will be followed-up by phone call or through electronic correspondence (RedCap) on post-operative days 3, 7, and 14. Participants in the study will be allowed to completed the questionnaires through RedCap with a +/- 2 day allowance on completion to avoid any study deviation. This follow-up will be obtained by the performing surgeons and/or the research office coordinator. At these planned follow-up intervals, patients will be evaluated using the Visual Analog Pain Scale (daily maximum and minimum) and visual analogue anxiety scale (daily maximum and minimum). In addition their pain control regimen (quantities of Tylenol, anti-inflammatories, and opioid pain medication) will be analyzed. Patients will be instructed to bring their medication bottles to their 3 week follow-up. Patient satisfaction with overall postoperative pain control will be measured based on subjective response. Finally, the duration of local anesthetic effect will be measured based on patient report.

Subject Information

Target accrual is the proposed total number of subjects to be included in this study at Mayo Clinic. A "Subject" may include medical records, images, or specimens generated at Mayo Clinic and/or received from external sources.

Target accrual: 130 patients (65 patients in each treatment arm) – this accounts for the necessary statistical power plus an anticipated approximately 20% dropout rate.

Subject population (children, adults, groups): Patients with medication-refractory erectile dysfunction undergoing penile prosthesis placement at Mayo Clinic in Rochester by Drs. [name], [name], and [name].

Inclusion Criteria:

- Men undergoing 3-piece inflatable penile prosthesis placement under general anesthesia at Mayo Clinic

 Rochester
- 2. \geq 18 years old

Exclusion Criteria:

- 1. History of opioid exposure within the preceding 90 days prior to surgery (based on patient-report, review of the electronic medical record, and NMP prescribing database review)
- 2. Current or prior history of alcohol or drug abuse (illicit or prescription)
- 3. History of chronic pain conditions (chronic musculoskeletal pain, fibromyalgia, central sensitization, chronic pelvic pain syndrome, etc.)
- 4. History of cardiac arrhythmia or untreated severe cardiovascular disease
- 5. Uncontrolled hypertension
- 6. Hepatic insufficiency
- 7. Renal insufficiency (CKD stage IIIa or greater)
- 8. Current anti-platelet or anti-coagulation therapy with plans to continue at the time of prosthesis placement
- 9. Poorly controlled diabetes mellitus (defined as HgbA1c > 8.5 within 30 days of surgery)
- 10. Concurrent adjunctive operative procedures planned at the time of penile prosthesis placement (examples: male urethral sling, Peyronie's disease straightening with penile plication or incision/grafting)
- 11. Concurrent non-prosthetic surgery planned at the time of penile prosthesis placement (examples: circumcision, hernia repair, hydrocelectomy, etc.)
- 12. Planned infrapubic or subcoronal incision at the time of penile prosthesis placement
- 13. Patients who will be undergoing prosthesis placement using local, monitored, or spinal anesthesia (i.e. non-general anesthesia)
- 14. Allergy or history of intolerance to any local anesthetic agents included in the protocol
- 15. History of prior penile prosthesis or artificial urinary sphincter surgery
- 16. Revision penile prosthesis surgery

Study Feasibility: At Mayo Clinic – Rochester, we perform approximately 200 penile prosthesis procedures per year amongst the three prosthetic surgeons, of which an estimated 90% are primary prosthesis placements. The majority of patients who are candidates for penile prosthesis placement will meet our inclusion criteria. Given that we will be comparing administration of two local anesthetics that are generally considered as standard of care, and the fact that our study protocol involves minimal additional time commitment on the part of the patient participants, we anticipate a high rate of patient willingness to participate in the trial. We anticipate study dropout to approach approximately 20%. Therefore, we estimate the study duration inclusive of patient accrual, data collection, and statistical analysis to be approximately 24 months.

Biospecimens

Not-applicable

Review of medical records, images, specimens

Check all that apply (data includes medical records, images, specimens).

Only data that exists before the IRB submission date will be collected.

Date Range for Specimens and/or Review of Medical Records:

Examples: 01/01/1999 through 12/31/2015, or all records through mm/dd/yyyy.

Note: The Date Range must include the period for collection of baseline data, as well as follow-up data, if applicable.

The study involves data that exist at the time of IRB submission **and** data that will be generated after IRB submission. Include this activity in the Methods section. Examples

- The study plans to conduct a retrospective chart review and ask subjects to complete a questionnaire.
- The study plans to include subjects previously diagnosed with a specific disease and add newly diagnosed subjects in the future.

The study will use data that have been collected under another IRB protocol. Include in the Methods section and enter the IRB number from which the research material will be obtained. *When appropriate, note when subjects have provided consent for future use of their data and/or specimens as described in this protocol.*

Enter one IRB number per line, add more lines as needed

🗌 Data	Specimens Data & Specimens	
🗌 Data	Specimens Data & Specimens	
🗌 Data	Specimens Data & Specimens	

Data Analysis

Power analyses may not be appropriate if this is a feasibility or pilot study, but end-point analysis plans are always appropriate even if only exploratory. Provide all information requested below, or provide justification if not including all of the information.

Power Statement: A total sample size of 110 (55 per arm) provides 90% power to detect a clinically relevant difference in discharge prescription opioids of 37.5 OME, based on a two-sample, two-sided, equal-variance t-test with significance alpha level 0.05, and assuming a common standard deviation of 60 OME. With an anticipated drop-out rate of 18%, total sample size will be 130 (65 per arm).

Data Analysis Plan:

Patient data will be recorded and stored in a study-specific database through RedCap. This database will be created by the primary investigator. At the completion of the study, statistical analyst support will be used to perform the final data analysis.

Preoperative data collection:

-State-Trait Anxiety inventory (attachment 1) -Pain Catastrophizing scale (attachment 2)

Postoperative days 3,7,14 data collection:

-Visual-analogue pain score (attachment 3)

-Visual-analogue anxiety score (attachment 4)

-Analgesic quantities (acetaminophen, meloxicam, ibuprofen, gabapentin, oxycodone, tramadol)

Endpoints

Primary:

1. Postoperative opioid pain medication use (number of oral morphine equivalents consumed per day and total number)

Secondary:

- 2. Postoperative pain scores (Maximum and minimum on visual analogue pain scale of 0-10) on postoperative days3, 7, 14
- 3. Postoperative non-narcotic pain medication use (non-steroidal anti-inflammatories, acetaminophen, gabapentin)
- 4. Postoperative anxiety scores (Maximum and minimum on visual analogue anxiety scale of 0-10) on postoperative days 0-7
- 5. Adverse perioperative events cardiovascular parameter changes
- 6. Patient satisfaction (subjective, patient reported)
- 7. Duration of pain control from local anesthetic

Attachments:

- -Visual-analog pain scale (attachment 1)
- -Visual-analog anxiety scale (attachment 2)
- -State-Trait Anxiety inventory (attachment 3)
- -Pain catastrophizing scale (attachment 4)
- -Perioperative analgesia protocol (attachment 5)
- -Preoperative, perioperative, and postoperative clinical variables of interest (attachment 6)
- -Proposed budget (attachment 7)

Anxiety Scores Prior to the procedure

Mark (X) the point on the scale that best describes how you are feeling at the moment. Use the Dowrick facial anxiety scale to assist you.

Edward Dowrick © 2016 Anxiety Level Self-assessment and facial anxiety scale female

After the procedure

Mark (X) the point on the scale that best describes how you are feeling at the moment. Use the Dowrick facial anxiety scale to assist you.

Edward Dowrick © 2016 Anxiety Level Self-assessment and facial anxiety scale female

State Trait Anxiety Inventory

How do you feel RIGHT NOW? Read each statement and select the number which most closely indicates how you feel right now. There are no right or wrong answers. Please give the answer which seems to describe your present feelings best.

	1	2	3		4		
	Not at all	A little	Some	what	Ver	y Much So	
1.	I feel calm		1	2	3	4	
2.	I feel secure		1	2	3	4	
3.	I feel tense		1	2	3	4	
4.	I feel strained		1	2	3	4	
5.	I feel at ease		1	2	3	4	
6.	I feel upset		1	2	3	4	
7.	I am presently worryin over possible misf	g ortunes	1	2	3	4	
8.	I feel satisfied		1	2	3	4	
9.	I feel frightened		1	2	3	4	
10.	I feel uncomfortable		1	2	3	4	
11.	I feel self confident		1	2	3	4	
12.	I feel nervous		1	2	3	4	
13.	I feel jittery		1	2	3	4	
14.	I feel indecisive		1	2	3	4	
15.	I am relaxed		1	2	3	4	
16.	I feel content		1	2	3	4	
17.	I am worried		1	2	3	4	
18.	I feel confused		1	2	3	4	
19.	I feel steady		1	2	3	4	
20.	I feel pleasant		1	2	3	4	

Total:

MAYO
P

$\overline{\mathbf{U}}$							
Ι	Copyri Michael	ght © 1995 JL Sullivan					
	PC	; S					
Client No.:	Age: Sex: M() F() Date:						
Everyone experie headaches, tooth pain such as illne	iences painful situations at some point in their lives. Such experiences may inc h pain, joint or muscle pain. People are often exposed to situations that may o ess, injury, dental procedures or surgery.	ause					
We are interested in the types of thoughts and feelings that you have when you are in pain. Listed below are thirteen statements describing different thoughts and feelings that may be associated with pain. Using the following scale, please indicate the degree to which you have these thoughts and feelings when you are experiencing pain.							
0 – notatali 1 –	– to a slight degree 2 – to a moderate degree 3 – to a great degree 4 – all	the time					
When	m I'm in pain						
1	I worry all the time about whether the pain will end.						
2	I feel I can't go on.						
3	It's terrible and I think it's never going to get any better.						
4	It's awful and I feel that it overwhelms me.						
5	I feel I can't stand it anymore.						
6	I become afraid that the pain will get worse.						
7	I keep thinking of other painful events.						
8	I anxiously want the pain to go away.						
9	I can't seem to keep it out of my mind.						
10	I keep thinking about how much it hurts.						
11	I keep thinking about how badly I want the pain to stop.						
12	There's nothing I can do to reduce the intensity of the pain.						
13	I wonder whether something serious may happen.						

Perioperative Analgesia Protocol

	POD													
	#1	#2	#3	#4	#5	#6	#7	#8	#9	#10	#11	#12	#13	#14
Minimum nain score														
(scale 0-10)														
(seule o ro)														
Maximum pain score														
(scale 0-10)														
Acetaminophen														
(Tylenol), number of														
tablets used														
Gabapentin														
(Neurontin), number														
of tablets used $(M, 1^{\circ})$														
Meloxicam (Mobic),														
number of tablets used														
of tablets used														
Other comments														
Other comments														
	1	1	1	1	1	1	1	1	1	1	1	1	1	1

Proposed Budget for Exparel IPP study

PERSONNEL (Period 1: 03/01/2021 - 03/01/2023)								
Name	Role			Amount				
	Principal Investigator							
	i inicipai investigator							
	Study Coordinator (12.5%			\$7,875.00				
	x 2 years)							
	Subtotal Direct Cost -			\$7,875.00				
	Personnel							
Internal Services (Period 1: MM/DD/YYYY - MM/DD/YYYY)								
	Entity			Amount				
	Miscellaneous Costs –			\$500.00				
	Men's Health Website							
	Statistical analyst support			\$6,000.00				
	Subtotal Direct Cost –			\$6500.00				
	Internal Service							
Total Direct Cost			\$14,375.00					
Indirect Rate			30.000%					
Total Indirect Cost			\$4,312.50					
Total Cost (Period 1	: MM/DD/YYYY - MM/DD/Y	\$18,687.50

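### The stated 40 mL for Arm 2 does not match its listed components, which add to 30 mL

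*Combined protocol and SAP*

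**What the plan says.** The two regimens are set out under Study Design and Methods in the combined protocol and SAP. The control arm is given as a single volume: "Arm 1 will receive 40 mL of ropivicaine to be used for local anesthetic infiltration". The experimental arm is given as a total followed by a breakdown in parentheses: "Arm 2 will receive 40 mL of Liposomal bupivacaine (20 mL Exparel + 10 mL 0.25% bupivacaine".

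The rest of the section does not add to that breakdown. On administration it says "Local anesthetic will be administered via a standard protocol at the time of penile prosthesis surgery", and then "The block itself will include pudendal, scrotal, dorsal penile, and inguinal nerve blocks", without volumes per site. On ordering it says "Two standardized order sets will be shared amongst the three performing surgeons", without giving the contents of either set. The Attachments list includes "Perioperative analgesia protocol (attachment 5"), but the supplied text under the Perioperative Analgesia Protocol heading is only a patient diary grid for pain scores and tablet counts.

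**The concern.** The total and the breakdown in the same sentence disagree, and this sentence is the only visible definition of the experimental regimen. If nothing is added beyond what is listed, no preparation can satisfy both figures.

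The possible explanations have different consequences:

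- **The total is wrong.** The listed drug amounts stand, but Arm 2 receives less volume than Arm 1 for the same four blocks. Volume then differs along with drug. The randomized comparison of the two regimens remains valid, but a difference is harder to attribute to the drug alone.
- **An inactive diluent was left out.** The volumes match and the listed drug amounts stand, in a mixture more dilute than the 30 mL sum would give.
- **A component volume is wrong, or an active component was left out.** The volumes match, but the amount of local anesthetic is not what the sentence lists.

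The primary endpoint (opioid use) and several secondary ones (pain scores, cardiovascular changes, duration of local anesthetic effect) all concern what this injectate does. The Background section also says the trial should help judge whether the added expense of liposomal bupivacaine is justified, so the amount of product used needs to be unambiguous.

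**Working it through.** **Inputs**, all from Study Design and Methods:

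- Arm 2 stated total: 40 mL
- Arm 2 listed components: 20 mL Exparel and 10 mL of 0.25% bupivacaine
- Arm 1 stated total: 40 mL (no concentration given)

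**Attempt to reproduce the stated total**

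- Sum of components: 20 + 10 = 30 mL. The stated 40 mL is not reproduced.
- Gap: 40 − 30 = 10 mL.
- Relative to the stated total: 10/40 = 25%. Relative to the listed components: 10/30 = 33%.

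Rounding cannot explain a gap of this size. The sentence is continuous running text with no table break or redaction mark, so a fault in reading the PDF is not apparent.

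**How far the possible readings differ.** Taking 0.25% as 2.5 mg/mL, 10 mL holds 10 × 2.5 = 25 mg of plain bupivacaine and 20 mL holds 20 × 2.5 = 50 mg. The rows below only show the spread. None is a proposal, and the list is not complete: more than one figure could be wrong, and an omitted active component cannot be quantified.

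| Reading | Total | Exparel share | Plain bupivacaine |
|---|---|---|---|
| Total wrong | 30 mL | 20/30 = 67% | 25 mg |
| Inactive diluent omitted | 40 mL | 20/40 = 50% | 25 mg |
| Plain bupivacaine volume wrong | 40 mL | 20/40 = 50% | 50 mg |
| Exparel volume wrong | 40 mL | 30/40 = 75% (30/20 = 1.5 times the listed volume) | 25 mg |

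**Between arms.** The comparison is 40 mL against 30 mL under the first reading and 40 mL against 40 mL under the others.

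**Search for a resolution.** No other part of the supplied text gives a diluent, a third component or another Arm 2 volume.

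**Effect on the power statement.** None: volume does not enter it. The inputs are a difference of 37.5 OME, an SD of 60 OME (37.5/60 = 0.625) and 55 per arm. With a two-sided alpha of 0.05, the t-test gives 90.1% power, in line with the stated 90%.

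**The case against.** The strongest reply is that this is a slip in the prose with no practical consequence. Ordering runs through two standardized order sets shared by all three surgeons, and the Background section describes liposomal bupivacaine as already routine there. The mixture may therefore be fixed in an operational document that is not shown. The analgesia attachment may also have held more than the diary grid and been lost when the PDF was read. And if an unlisted diluent is used, both figures are correct and the fault is an omission rather than a contradiction.

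Much of this is fair. Inconsistent preparation cannot be inferred from the documents, and the unseen order sets or attachment may well specify one composition. That would still leave the protocol sentence uncorrected: order sets have to agree with the protocol, and the text does not show which figure they follow. The diluent explanation is possible, but nothing written supports it over the others.

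A second reply is that equal volume is nowhere stated as a design requirement and that, with no ropivacaine concentration given, drug amounts cannot be compared between arms from this text anyway. This stands in part. The volume question is secondary to the arithmetic, which is why the request is only to state the intent.

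**Conclusion.** The concern holds. The Arm 2 total exceeds its listed components by 10 mL (25% of the stated total), and the supplied text does not explain the difference. The conclusion rests on two assumptions: that the sentence was read correctly from the PDF, and that the parenthesis is meant as the full composition. If the second is wrong, the sentence is incomplete and still needs correcting.

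It must be fixed because the experimental regimen cannot be reproduced as written, and because a reader cannot tell whether the arms differ in volume as well as drug. The sentence applies to all 65 patients planned for Arm 2, but no harm, bias or variation in preparation is shown.

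**What to change.** In Study Design and Methods, reconcile the Arm 2 total with its components so that the listed parts account for the whole volume, naming every component. Confirm that both order sets agree with the corrected sentence. Add a statement of whether total volume is meant to be equal between arms. The investigators decide which figure is correct; this review takes no position on it.

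The cost is a correction to one sentence, a short added statement, a check of two order sets, and the IRB modification that the protocol template requires for any revision. Sample size and the analysis plan do not change.

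### Surgeons who know the allocation may collect the day 3, 7 and 14 outcomes: a modest but avoidable risk of observer bias

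*Combined protocol and SAP*

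**What the plan says.** All but the last two points below come from Study Design and Methods.

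- **Who knows the arm.** "The patient will be blinded to which study arm he is randomized to, but the surgeon will be aware (i.e. single blind". The surgeon also orders the allocated agent, so this knowledge is built into the procedure.
- **How follow-up is done.** "The patients will be followed-up by phone call or through electronic correspondence (RedCap) on post-operative days 3, 7, and 14".
- **Who does it.** "This follow-up will be obtained by the performing surgeons and/or the research office coordinator".
- **What protects the data.** "They will also receive a medication log to track their narcotic intake until post-operative day 14". Patients may complete the questionnaires themselves in REDCap, but this is optional. Finally, "Patients will be instructed to bring their medication bottles to their 3 week follow-up".
- **What is collected.** The Data Analysis Plan lists pain score, anxiety score and analgesic quantities for the same three days. The analgesics include oxycodone and tramadol.
- **What it feeds.** The primary endpoint, under Endpoints, is postoperative opioid use, defined as "number of oral morphine equivalents consumed per day and total number".

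The documents do not require the collector to be unaware of the arm. They do not say whether the coordinator is unaware of it, and they do not say whether the log or the phone answer is the source record.

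**The concern.** Read together, these statements allow the person who chose and gave the treatment to ask the patient about pain, anxiety and tablets taken, and to write down the answers. Blinding the patient does not stop a caller from prompting, probing or transcribing differently by arm.

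The Background section records that the investigators' experience already favours liposomal bupivacaine. That does not show that bias will occur, but it does mean the possible collectors are not without a prior view.

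A difference in elicitation between arms passes straight into the estimated treatment effect. A shift towards the hypothesis raises the false-positive rate, a shift against it lowers power, and an equal shift in both arms does nothing to the comparison. Analysis cannot remove such a shift once the data are collected.

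**Working it through.** **Reading.** The surgeon knows the arm. The surgeon may make the day 3, 7 and 14 contacts. Those contacts may be by phone, and they yield the opioid quantities for the primary endpoint. Each step is stated in the plan, and no other passage closes the route. The point therefore rests on the text; the arithmetic below only shows scale.

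**The plan's own figure.** Inputs from the Power Statement: a "clinically relevant difference in discharge prescription opioids of 37.5 OME", common SD 60 OME, two-sided alpha 0.05, equal-variance t-test, 55 per arm.

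- The normal approximation gives 54 per arm. The exact t calculation gives 54.8, so 55.
- Standard error = SD × √(2/n) = 60 × √(2/55) = 11.44.
- Exact power at 55 per arm is 90.1%. The stated 90% reproduces.

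**Illustration of a biased contact.** These inputs are assumptions, not figures from the documents:

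- one third of patients are phoned by a surgeon;
- each such patient in one arm is shifted by 7.5 or 15 OME relative to the other arm;
- the SD of 60, which the plan gives for discharge prescriptions, also applies to opioids consumed. The documents give no SD for consumption, so 40 and 80 are shown as well.

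Mean shift = per-patient shift × exposed fraction: 7.5 × 1/3 = 2.5 OME, and 15 × 1/3 = 5 OME. As a share of the design difference, 2.5/37.5 = 6.7% and 5/37.5 = 13.3%.

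The rejection rate comes from the noncentral t with 108 degrees of freedom and noncentrality = mean shift / standard error. With no true effect:

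| SD (OME) | Standard error | Mean shift 2.5 | Mean shift 5 |
|---|---|---|---|
| 40 | 7.63 | 6.2% | 10.0% |
| 60 | 11.44 | 5.5% | 7.2% |
| 80 | 15.26 | 5.3% | 6.2% |

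A simulation of 200,000 runs at SD 60 with one third exposed gave 5.48% and 7.13%, in agreement with the table.

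If the shift runs against a true difference of 37.5 OME (SD 60), the apparent difference is 35 or 32.5 OME. Power then falls from 90.1% to 85.8% or 80.4%.

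Only the product of shift and exposed fraction matters. Half the patients exposed at 10 OME also gives a mean shift of 5 and a rate of 7.2%. Bias in the pain and anxiety scores is not quantified, because the documents give no SD for them.

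**The case against.** The other side has a fair case.

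- **It is a permission within a declared single-blind design.** The wording is and/or, so the coordinator could make every contact, and nothing says the surgeons will. True, but declaring that the surgeon knows the arm explains why he must know it to operate. It does not explain why he should record the endpoint.
- **The remaining channel is narrow.** The source is a blinded patient with a log, optional REDCap entry and a bottle check. The Perioperative Analgesia Protocol has a daily grid for days 1 to 14 with minimum and maximum pain. In-hospital opioid use, if it counts and comes from the chart (the documents do not say), would bypass these calls. This stands, and it is why the risk is called modest. The protection is not complete: REDCap is optional, reconciliation of bottles with reported use is not described, and the legible part of the grid shows no anxiety row. A bottle count cannot verify a pain or anxiety score.
- **The shifts are invented.** Also true. A shift of 15 OME is 40% of the design difference (15/37.5) in each exposed patient, and nothing in the documents supports it. The 10.0% figure needs both that shift and the lowest assumed SD. The smaller case at the plan's SD moves the error rate only from 5% to 5.5%.
- **The fix may not give a blinded collector.** The coordinator's status is not stated, and the surgeons' clinical contact can still colour what patients report. Both limits stand. They call for a fallback, not for keeping surgeons as collectors.

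**Conclusion.** The concern holds. The plan permits a person who knows the allocation to elicit and record the primary endpoint and the subjective secondary scores, although it already names routes that avoid this. Confidence is high for what the text permits. It does not extend to any particular amount of bias, because neither size nor direction can be derived from the documents.

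Given the safeguards, the effect is probably small. Under the stated assumptions at the plan's own SD, the false-positive rate rises by about half a point to two points. Much larger inflation would need all patients to be exposed, and that is not claimed. This is not a fatal flaw. It should be changed because it touches the primary endpoint and costs little to prevent.

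**What to change.** **Change.** In the follow-up paragraph of Study Design and Methods:

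1. Remove the performing surgeons as collectors of the day 3, 7 and 14 data. They keep clinical contact but do not record trial outcomes.
2. Make REDCap self-completion the default.
3. Have the coordinator make any phone contact with a fixed script, transcribe the patient's log, and not view the allocation or the order set. If the three-week bottle check is trial data, the coordinator records it too.
4. Add two REDCap fields for each contact: collector and route.
5. If the coordinator cannot be kept unaware of the allocation, rely on self-completion and verbatim transcription of the log.

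**Cost.** One wording change, one access rule and two database fields. The upper bound on calls, with no dropout and no REDCap use, is 130 × 3 = 390, or 130 × 4 = 520 with the bottle check. The Proposed Budget has the coordinator at 12.5% for two years. Assuming a 40-hour week, that is 0.125 × 40 × 52/12 = 21.7 hours a month. Assuming 10 to 20 minutes per contact:

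| Contacts | Over 24 months | Over 18 months |
|---|---|---|
| 390 | 16.25 a month, 2.7 to 5.4 h | 21.7 a month, 3.6 to 7.2 h |
| 520 | 21.7 a month, 3.6 to 7.2 h | 28.9 a month, 4.8 to 9.6 h |

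The 18-month column matters because the planned 24 months also cover analysis. The heaviest case uses 9.6/21.7 = 44% of the assumed hours, before consent work, baseline questionnaires and repeat call attempts.

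**Downside.** Patients who do not use REDCap still need a call, so some completeness may be lost without the surgeons, in a trial that expects 18% to 20% dropout.
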